2.1 Risks, Side Effects, and/or Discomforts

There are minimal risks to participating in this study. There is a minimal risk of visual or physical discomfort during the vision tests (though these tests are similar to standard vision testing). Participants might become uncomfortable or dizzy while using the device. We will do everything we can to ensure comfort, and the tests will be stopped if there is discomfort.

There is also the possibility of loss of confidentiality. All information will be stored within HIPAA compliant computers that are protected and deemed safe for university/hospital researcher data storage. We will not be sharing your data for anything other than reviewing the results for this study. We will also remove any identifying information from your information used for analysis of the computer program.

There is a mild risk of falls during any balance, gait, or mobility assessments. There will be a licensed PT supervising all mobility tasks and will assist to prevent a fall. If necessary, there is an overhead, body-weight support device that may be utilized for additional protection.

While we believe the risk of injury during this study is minimal, please be advised that Brooks Rehabilitation will manage the participant's care consistent with the management of all treatment-related adverse events. The participant's insurance will be responsible for any medical cost including deductibles, co-insurance, or co-payments. Any injury requiring medical care will be reported to the Institutional Review Board providing oversight of this study.

2.2 Alternatives to Participation

This study is for research purposes only. The alternative is to not participate in this study. By choosing not to participate, your care will not be altered in any way.

2.3 Cost

There is no monetary compensation for participation in this study. We will provide a travel reimbursement for enrolled participants of \$25 per visit, up to \$50 per participant. This will be paid to the participant in the form of a Visa gift card.

Section 3: Monitoring/Reporting of AE/SAE

Records of participation in this study will be held confidential except when sharing the information is required by law or as described in this informed consent. The Investigator, the sponsor or persons working on behalf of the sponsor, and under certain circumstances, the United States Food and Drug Administration (FDA) and the Institutional Review Board (IRB) will be able to inspect and copy confidential study-related records. This means that absolute confidentiality cannot be guaranteed. If the results of this study are published or presented at meetings, they will be de-identified.

Participant vitals and visual and physical comfort will be monitored by study staff throughout the assessments. Participants will self-report any visual or physical discomfort during the weekly check ins with a study team member. Any abnormal or adverse responses to utilizing the device will be reported to the study physician who will provide medical recommendations for proceeding or terminating use of the device. Repeated and unresolved abnormal responses will result in withdrawal from the study under the advisement of the study physician. All adverse events will be tracked and reported to the IRB, primary investigator, and study physician.

Section 4: Study Oversight

[name], who has been practicing for 12 years and participating in research for 10 years, will serve as the principal investigator and maintain administrative oversight of this study, ensuring compliance with this protocol, related policies and procedures of Brooks Rehabilitation, and relevant rules and regulations.

Collection, recording, and reporting of data will be accurate and will ensure the privacy, health and welfare of participants. All study documents and procedures will be made available for monitoring, auditing, IRB review and regulatory inspection as required by the IRB and/or by law. The study will be discontinued if the principal investigator, the Brooks Center for Low Vision, or the IRB determines necessary. The principal investigator will promptly inform the IRB and provide the reason(s) for the termination or suspension of the study.

Circumstances that may warrant termination include, but are not limited to:

- Determination of unexpected, significant or unacceptable risks to participants.
- Insufficient adherence to protocol requirements.
- Data that are not sufficiently complete and/or evaluable.
- Determination of futility.

The principal investigator may terminate a participants' participation in the study if:

- Any situation occurs such that continued participation in the study would not be in the best interest of the participant.

Section 5: Data Management

Data will be collected and stored on a HIPAA-compliant, encrypted, password-protected server at Brooks Rehabilitation that is only accessible to Brooks Rehabilitation Clinical Research Center or Brooks Center for Low vision authorized personnel. Paper copies will be kept in a locked storage cabinet within the Brooks Rehabilitation Clinical Research Center.

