TITLE	Assessing the Impact of eSight Go At-Home Usage in Individuals with Visual Impairment
SHORT TITLE	eSight
PROTOCOL NO.	00085670
SPONSOR	Gentex Corporation
INVESTIGATOR	[name]
ADDRESS	[name]
[contact]
EMAIL	[contact]
VERSION	7.0
DATE	04/18/2025

Contents

Brief Overview	3
Section 1: Procedures	3
1.1 Screening/Recruitment Procedures.....	3
1.1.1 Inclusion/Exclusion Criteria.....	3
1.2 Informed Consent Process	4
1.3 Assessments.....	4
1.4 Intervention	5
1.5 Data Analysis.....	5
Section 2: Risk Information	6
2.1 Risks, Side Effects, and/or Discomforts	6
2.2 Alternatives to Participation	6
2.3 Cost	6
Section 3: Monitoring/Reporting of AE/SAE	6
Section 4: Study Oversight	7
Section 5: Data Management	7

Brief Overview

The purpose of the study is to assess the effect of the updated version of Gentex's device, eSight Go, an image-enhancing wearable device to assist those with vision impairment. The study will comprise at least 50 vision impaired individuals to evaluate the efficacy or improvements in visual, quality of life, and mobility arising from the use of eSight Go. The primary aim of the study is to measure the effect of eSight Go on visual acuity, reading performance, and quality of life. The secondary aim is to measure the impact of eSight Go on mobility, balance, cybersickness, and user satisfaction. The study assessments will take place at the Brooks Rehabilitation Clinical Research Center at 4 time points:

- 1) at visit 1 before using the device;
- 2) during visit 1, while using the device;
- 3) at visit 2, while using the device; and,
- 4) during visit 2 without the device.

Participants will receive a personal eSight device and comprehensive training on its operation at visit 1. They will then use the unit in daily living, such as home, work, or school settings, over a period of 4 weeks, and then return for visit 2. If prescription lenses are determined to be needed to correct refractive error, visit 1 will be divided into 2 visits to allow time for the lenses to be ordered prior to starting the at-home trial period.

Section 1: Procedures

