1.3 Assessments

Participants will complete assessments four times, twice at visit 1 and twice at visit 2, except for the OMCT and the refraction which will only be performed once at visit 1.

Study Timeline

5/2025	5/2025-4/2026			5/2026-7/2026
Open enrollment	Visit 1	4 Weeks At Home Usage	Visit 2	Complete Analysis, Study Close Out

Assessments will include the following procedures:

Primary Aim Assessments (Visual)

- Early Treatment Diabetic Retinopathy Study Chart (ETDRS)
- MNREAD
- MARS Test
- NEI VFQ-25
- Reading Behavior Inventory
- Refraction Test

Secondary Aim Assessments (Mobility & Cognitive)

- Dynamic Gait Index
- Timed Up and Go
- Spatiotemporal Gait Kinematics
- OMCT
- PROMIS Short Form v2.0 - Cognitive Function 8a

Questionnaires

- Demographic information
- Ophthalmic History
- 36-Item Short Form Health Survey
- Cybersickness in Virtual Reality
- Device Usage Willingness and Participation
- Activities Balance Confidence Scale

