1.4 Intervention

Participants will take the device home for 4 weeks to use in daily living, such as the home and community settings. There will be regular follow-up phone calls once per week from a member of the research team (e.g., an occupational therapist, or low vision therapist) who is familiar with the device to assist with possible troubleshooting as well as device use strategies. The follow up calls will also collect information about device use time and activities. The device will be returned at visit 2.

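### Withdrawing participants with repeated, unresolved reactions to the device leaves them without cybersickness or satisfaction scores after home use, so visit 2 results probably look too favourable

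*Protocol*

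**What the plan says.** Section 3 of the protocol describes two consequences of a bad reaction. First, the reaction is reported to the study physician, who "will provide medical recommendations for proceeding or terminating use of the device". Second, "Repeated and unresolved abnormal responses will result in withdrawal from the study under the advisement of the study physician".

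The Brief Overview sets the aims affected: "The secondary aim is to measure the impact of eSight Go on mobility, balance, cybersickness, and user satisfaction". Section 1.3 sets the schedule: "Participants will complete assessments four times, twice at visit 1 and twice at visit 2", with the OMCT and the refraction as the only exceptions. The instruments listed there include the Cybersickness in Virtual Reality questionnaire and the Device Usage Willingness and Participation questionnaire. The second is the closest listed instrument to user satisfaction.

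Between the visits there are weekly calls. Section 1.4 gives them a troubleshooting role and adds: "The follow up calls will also collect information about device use time and activities". Section 3 adds self-reported visual or physical discomfort at the weekly check-ins, and tracking of all adverse events. On the equipment, Section 1.4 says: "The device will be returned at visit 2".

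**The concern.** The withdrawal rule selects participants on something very close to what the cybersickness questionnaire measures. Section 2.1 foresees discomfort and dizziness while the device is in use. A participant in whom this keeps recurring and does not resolve leaves the study, while one with a milder or resolved reaction stays and is scored at visit 2.

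Every participant receives the device, so no comparison group offsets this selection. Section 1.5 relies on changes from pre- to post-testing, which need a post-test value. The post-home-use results on cybersickness and satisfaction would therefore describe the people who tolerated the device better and could be read as describing everyone who took it home.

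The protocol itself causes this loss. An analysis plan may say how missing scores are handled, but it cannot collect scores from people the protocol has already released.

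**Working it through.** The protocol states no withdrawal rate, effect size or standard deviation, so there is no figure of its own to reproduce. The check is mainly a comparison of the text, followed by counts and an illustration under stated assumptions.

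**Text, side by side**

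1. Section 3 names ending device use and ending study participation as different outcomes, and it prescribes the second for repeated and unresolved reactions.
2. The Brief Overview and Section 1.3 give four time points: visit 1 without and with the device, and visit 2 with and without it. Visit 2 is the only scheduled assessment after home use.
3. No exit visit or closing questionnaire is described. The weekly calls are said to cover troubleshooting, use time, activities and discomfort, but not the two questionnaires.
4. It follows that a participant withdrawn while the device is at home has both visit 1 time points and neither visit 2 time point. This is inferred from the schedule. The protocol does not say it outright.

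**Counts**

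Inputs: planned minimum N = 50 (Brief Overview); number withdrawn k = 1, 3 or 5 (assumed).

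- Time points lost per withdrawal: 2 of 4.
- Share absent at visit 2 = k/50: 1/50 = 2%, 3/50 = 6%, 5/50 = 10%.
- Remaining with visit 2 scores = 50 − k: 49, 47, 45.

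**Illustrative effect on a mean score**

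Let w = k/50, and let g be the gap between withdrawn participants and completers in SD units. The mean over everyone is (1 − w) × completer mean + w × withdrawn mean, so the completer mean is too favourable by w × g. The standard error of the completer mean is 1/√(50 − k) SD. All values of k and g are assumed.

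| k | w | g = 0.5 | g = 1.0 | g = 2.0 | standard error |
|---|---|---|---|---|---|
| 1 | 0.02 | 0.01 | 0.02 | 0.04 | 0.143 |
| 3 | 0.06 | 0.03 | 0.06 | 0.12 | 0.146 |
| 5 | 0.10 | 0.05 | 0.10 | 0.20 | 0.149 |
| 10 | 0.20 | 0.10 | 0.20 | 0.40 | 0.158 |

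**Illustrative effect on a proportion**

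Suppose 10% of completers report marked cybersickness and every withdrawn participant would have done so (both assumed). The rate among all 50 is (0.10 × (50 − k) + k)/50:

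- k = 1: (4.9 + 1)/50 = 11.8%
- k = 3: (4.7 + 3)/50 = 15.4%
- k = 5: (4.5 + 5)/50 = 19.0%
- k = 10: (4.0 + 10)/50 = 28.0%

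The direction is the same throughout. The size runs from negligible to material, depending on figures the protocol does not give.

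**The case against.** The strongest reply is that this is a narrow clause protecting participants. It needs reactions that are both repeated and unresolved, and it acts on the physician's advice. The step before it already allows the device to be stopped without withdrawal. The text does not forbid closing questionnaires, and it does not say how a withdrawn participant returns the device, so an assessment might take place then. Intolerance is also recorded through the visit 1 on-device scores, the weekly reports and the adverse event records.

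The narrow scope stands, and so does the partial capture. Neither supplies a score after home use on the instruments that serve these aims. The physician has some discretion, but the operative wording is that withdrawal will follow, and no option to stay for assessment is stated. Safety requires ending exposure to the device. It does not require ending a phone questionnaire or an off-device visit.

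Two further points stand as limits on the remedy:

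- A participant who feels unwell may still leave by choice. Section 1.1.1 covers enrolled participants who become unable or unwilling to continue. The selection would be reduced but not removed.
- A score taken when use stops differs from the visit 2 on-device score in timing and device state, and in mode if it is taken by phone. It supplements that score and does not replace it.

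The unknown size also stands. In the illustration, 5 withdrawals with a 1 SD gap shift the mean by 0.10 SD, which is less than one standard error (0.149 SD).

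**Conclusion.** The concern holds. As written, Section 3 removes the participants who tolerate the device worst from the only assessment after home use. Visit 2 cybersickness and satisfaction scores will therefore probably look better than among all who took the device home.

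The direction rests on the removal criterion being a bad reaction to the device. The loss of scores rests on reading the fixed schedule as complete, with no unstated exit assessment. Treating the device-willingness questionnaire as the satisfaction measure is also an assumption, since no instrument of that name is listed.

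The size is unknown. Each withdrawal costs 2% of the visit 2 sample at the minimum of 50, and the assumed cases shift a mean by 0.01 to 0.40 SD. The point is limited to cybersickness and satisfaction and does not extend to gait or off-device vision scores. It is worth correcting because an analysis plan cannot repair it and the correction is cheap.

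**What to change.** - **Reword the rule.** In Section 3, let repeated and unresolved abnormal responses end device use, on the study physician's advice. The participant then stays in the study unless he or she declines, or the principal investigator ends participation under the existing ground in Section 4: "Any situation occurs such that continued participation in the study would not be in the best interest of the participant".
- **Collect the scores.** At the contact where use stops, give the cybersickness and device-willingness questionnaires, by phone if needed. Invite the participant to the off-device visit 2 assessments when the device is returned.
- **Report the count.** Give the number stopped for intolerance beside the visit 2 scores.

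The cost is one reworded sentence and two short questionnaires for those who stop. The weekly calls are already planned, and the device has to come back in any case. There are downsides: some burden on a participant who has felt unwell and may decline, a score taken at stopping and not at 4 weeks, and a possibly less favourable cybersickness result.

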1.5 Data Analysis

Data will be captured during all assessments. Data will be compared against normative values, when available and change scores from pre- to post-testing will be calculated for absolute differences. Continuous data will be compared pre- to post-testing using independent samples t-tests. Ordinal data, including all questionnaires, will be evaluated using a Mann-Whitney U test.

Section 2: Risk Information

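### Withdrawing people with unresolved reactions to the device, with no cybersickness score at stopping, tilts the visit-2 cybersickness result in the device's favour by an unknown, possibly small, amount

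*Protocol*

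**What the plan says.** The Brief Overview of the protocol names the outcome: "The secondary aim is to measure the impact of eSight Go on mobility, balance, cybersickness, and user satisfaction". Of its four time points, the third is the only one taken on the device after the 4 weeks at home: "at visit 2, while using the device".

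Section 1.3 lists a cybersickness questionnaire and sets the timing for everything except the cognitive screen and the refraction: "Participants will complete assessments four times, twice at visit 1 and twice at visit 2".

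Between visits there are weekly calls. Section 1.4 says of them: "The follow up calls will also collect information about device use time and activities". Section 3 adds self-reported visual or physical discomfort at the same contacts, and the tracking of all adverse events.

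Section 3 has two steps for abnormal responses to the device. They go first to the study physician, "who will provide medical recommendations for proceeding or terminating use of the device". Then: "Repeated and unresolved abnormal responses will result in withdrawal from the study under the advisement of the study physician". Section 4 separately lets the principal investigator end participation where "Any situation occurs such that continued participation in the study would not be in the best interest of the participant".

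Section 1.5 gives the analysis: "Ordinal data, including all questionnaires, will be evaluated using a Mann-Whitney U test".

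**The concern.** The withdrawal rule acts on responses close to what the cybersickness questionnaire measures; Section 2.1 itself expects that some users may feel uncomfortable or dizzy. Section 3 distinguishes stopping the device from leaving the study, and prescribes the latter for the unresolved cases. Leaving the study means no visit 2, and the schedule holds no other point at which the questionnaire is completed.

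The missing scores would therefore not be a random loss. They would come disproportionately from those who fared worst, and the remaining visit-2 scores would look better than home use really was. Visit 2 is the only scored look at cybersickness after home use, so nothing on the same scale replaces it. Analysis can handle missing data in various ways, but whether a score is taken when use stops is decided by the protocol during data collection.

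**Working it through.** The plan gives no figure to reproduce: no withdrawal rate, no expected cybersickness rate and no derivation of the sample size. The check has two parts.

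**1. Schedule against withdrawal rule.**

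| Point in time | Cybersickness questionnaire? | Available for a person withdrawn during home use? |
|---|---|---|
| Visit 1, off device | yes (1.3) | yes |
| Visit 1, on device | yes (1.3) | yes |
| Weekly calls | none named; use time, activities, discomfort (1.4, Section 3) | discomfort report only |
| When use stops | none named | no score; adverse event record |
| Visit 2, on device | yes (1.3) | no |
| Visit 2, off device | yes (1.3) | no |

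Keeping such a person in the study would not by itself supply the visit-2 on-device score, since someone taken off the device for unresolved symptoms could not properly be put back on it. It would keep only the off-device assessments. The main gap is thus a score at the moment of stopping.

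**2. Size, on assumptions.** Only N = 50 is from the protocol (its stated minimum). Assume k people are affected and w of them are withdrawn, with no other losses.

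Share seen at visit 2 = (k − w)/(50 − w); true share = k/50.

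| k (true share) | w = 1 | w = 2 | w = 3 | w = 5 |
|---|---|---|---|---|
| 5 (10%) | 4/49 = 8.2% | 3/48 = 6.3% | 2/47 = 4.3% | – |
| 10 (20%) | 9/49 = 18.4% | 8/48 = 16.7% | 7/47 = 14.9% | 5/45 = 11.1% |
| 15 (30%) | 14/49 = 28.6% | 13/48 = 27.1% | 12/47 = 25.5% | 10/45 = 22.2% |

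For k = 10 the shortfall is 1.6 points with 1 withdrawn, 3.3 with 2 and 8.9 with 5.

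On a continuous scale, suppose scores are normal and the withdrawn share p holds the highest ones. The mean of those remaining is then lower by φ(z₁₋ₚ)/(1 − p) standard deviations: 0.05 for 1 of 50, 0.09 for 2, 0.20 for 5 and 0.35 for 10. This is the extreme case, because it takes every withdrawn person from the top of the distribution.

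**Withdrawals for other reasons.** Let a of the w withdrawn be affected by cybersickness. The share seen is (k − a)/(50 − w). With k = 10 and w = 5: a = 5 gives 11.1%, a = 2 gives 8/45 = 17.8%, and a = 1 gives 9/45 = 20%, that is, no bias. The result leans in the device's favour when cybersickness is more common among the withdrawn than among everyone. The trigger makes that likely but does not fix how much more common.

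**What an exit score adds.** With k = 10, w = 5 and all five affected, exit scores from all five give 10/50 = 20%. If two decline, the share is (5 + 3)/(45 + 3) = 8/48 = 16.7%, against 11.1% without exit scores. This assumes that the phone score identifies these people as affected.

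**The case against.** The strongest reply is that little is lost. Withdrawal needs responses that are both repeated and unresolved, and follows the physician's advice; it is a last safety step. It covers any abnormal response, not only cybersickness. Everyone is scored off and on the device at visit 1, and weekly reports and adverse event tracking record what happens afterwards. Section 2.1 calls the risks minimal, so few may be withdrawn. The 95% half-width for 10 of 50 is 1.96 × √(0.2 × 0.8/50) = 11 points, wider than the 8.9-point shortfall with 5 withdrawn. A score recalled by phone is no substitute for one taken on the device after 4 weeks.

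Most of this stands, and it limits the point. A reader might infer that withdrawal is automatic, or that these people's harm disappears from the record. The documents support neither: the physician advises, and three other sources still capture the harm. Nor does the protocol say in words that no questionnaire is taken at stopping; that follows from reading the fixed schedule together with the withdrawal rule.

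Two parts of the reply do not remove the concern. Sampling error has no preferred direction, whereas this loss does, so a wide interval is no defence against it. And the other sources are either earlier than home use (visit 1) or not on the questionnaire's scale (discomfort reports, adverse events), so they cannot correct the visit-2 score.

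**Conclusion.** The point holds in a limited form and is worth acting on because the remedy is cheap. As written, the plan makes visit-2 on-device cybersickness scores missing for reasons tied to the outcome, and the result will lean in the device's favour. The amount is unknown. With 10 of 50 affected and 1 or 2 of them withdrawn, 20% would be seen as 18.4% or 16.7%, a small change; with 5 withdrawn it would be seen as 11.1%. These figures assume that every withdrawn person had cybersickness.

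A reader might go further and infer that the cybersickness aim fails, or that an exit score would restore the visit-2 result. Neither follows. The visit-1 comparison is untouched, large effects need many withdrawals nearly all for cybersickness, and a phone score is recalled, taken off the device and earlier than 4 weeks. It supplements the visit-2 score without replacing it.

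The choice of test is a separate defect: Mann-Whitney is for independent groups, and here the same people are measured repeatedly.

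**What to change.** Replace the withdrawal sentence in Section 3 with wording such as:

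> If abnormal responses recur and do not resolve, the participant stops using the device on the study physician's advice. The cybersickness questionnaire is completed by phone at or near the time of stopping, about the last period of use. The participant is invited to visit 2 for the off-device assessments only, unless consent is withdrawn or the principal investigator ends participation in the participant's best interest.

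For the analysis, in Section 1.5 or the SAP:

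- Report the number who stopped for discomfort beside the visit-2 cybersickness result.
- Use the exit score only in a supporting analysis, as the last score relating to device use for those who stopped, and say that it is a different kind of score.
- Separately, compare cybersickness within the same people with a Wilcoxon signed-rank test in place of Mann-Whitney.

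The cost is a few sentences and one short phone questionnaire per person who stops, at or near a weekly call already planned. Nobody is put back on the device, the physician can still end its use at once, and the investigator keeps the power in Section 4 to end participation. The drawbacks are that some who stop will decline, and that the supporting analysis mixes two kinds of score.
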